Analyses are conducted at the individual employee level and at the worksite level. The treatment period in our phase 2 analysis is defined as the 36-month period spanning January 2015 through December 2017. (In comparison, the phase 1 analysis spanned January 2015 through mid-2016).

A. Intention-to-treat analysis

In the individual-level intention-to-treat (ITT) analysis, our goal is to estimate the average effect of a worker being randomized into a treatment worksite on outcomes of interest. Given that the

⁹ Zubizarreta JR. Stable weights that balance covariates for estimation with incomplete outcome data. *Journal of the American Statistical Association*. 2015 Sep;110(511):910-922; Wang X, Zubizarreta JR. Minimal approximately balancing weights: Asymptotic properties and practical considerations. *Biometrika*. 2017;103(1):1-22; Hirshberg DA, Zubizarreta JR. On two approaches to weighting in causal inference. *Epidemiology*. 2017;28(6):812-816.

treatment is implemented at the worksite level and that there are likely fixed costs of the program, the ITT estimates (and the worksite level analysis) are informative.

We use a base specification that includes a dose-response measure of the effect of exposure to the intervention (as measured by time worked). This specification captures the overall effect of randomization into treatment as well as how the effect of randomization to a treatment site varies with additional exposure to the treatment.

$$Y_{ijt} = \beta_0 + \beta_1 TREATMENT_{jt} + \beta_2 TIME_WORKED_{ijt} + \beta_3 TREATMENT_{jt} * TIME_WORKED_{ijt} + \beta_4 X_{ijt} + \varepsilon_{ijt} \quad (1)$$

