The key identifying assumption is that the only mechanism through which being employed in a treatment worksite affects outcomes is through the availability of the wellness program. There are two threats to this assumption. First, to the extent that covariates were not balanced at baseline and those covariates affect the outcomes of interest, that imbalance could bias our estimates. We control for observed covariates and apply weights to balance covariates between treatment and control. Despite these adjustments, unobserved covariates might still be imbalanced.

Second, to the extent that the wellness program affected hiring or tenure of employees, their presence in the data set may be endogenously determined. We address the issue of endogenous entry by pre-specifying a subsample of those who were already employed at the time the intervention began. We defined this more restrictive “stable employment” subsample as comprising employees who had worked continuously for 13 weeks prior to the wellness program. This comes at a cost of reducing the overall sample size. Our goal in choosing the definition for this subsample was to balance the costs and benefits, as detailed in Appendix 2.

In this stably employed subsample, however, exit from the firm's workforce is still potentially endogenous. We deal with this concern in two ways. First, we will test balance on exit between treatment worksites vs. from control worksites overall and for subgroups. Indeed, tenure and time worked are among our primary outcomes. To the extent that we observe any unbalanced exit, we will perform a bounding exercise (assuming that those who exited have outcomes working against any observed effects of the intervention).

D. Subgroup analyses

We pre-specified three subgroup analyses. We selected these subgroups based on differences in key outcomes within the control group for those with different baseline characteristics, such as differences in medical spending by age or in reported exercise by sex (**Table 11**).

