We will analyze how the effect of the wellness program varies along 3 pre-specified dimensions: age (less than 40 years or 40 and above), sex (male or female), and employment status (full-time vs. part-time). In our model, these subgroup analyses are implemented using a set of two-way interaction terms and a triple interaction term. Equation 5 below shows these interaction terms in our ITT framework, using the subgroup analysis on age as the representative equation, where $age40_{it}$ is defined as 1 if the individual is age 40 years or older, and 0 otherwise.

$$\begin{aligned}
 Y_{ijt} = & \beta_0 + \beta_1 TREATMENT_{jt} + \beta_2 TIME_WORKED_{ijt} + \beta_3 Age40_{it} \\
 & + \beta_4 TREATMENT_{jt} * TIME_WORKED_{ijt} + \beta_5 TREATMENT_{jt} * Age40_{it} \\
 & + \beta_6 TIME_WORKED_{ijt} * Age40_{it} + \beta_7 TREATMENT_{jt} * TIME_WORKED_{ijt} * Age40_{it} \\
 & + \rho X_{ijt} + \varepsilon_{ijt}
 \end{aligned} \tag{5}$$

In this model, the coefficient on the triple interaction term, β_7 , represents the marginal effect of an additional unit of exposure (as measured by time worked) among employees 40 years or older who were randomized into treatment. For those under age 40, the effect of the wellness program is represented by $\beta_1 + \beta_4 * Exposure$. For those over age 40, the effect of the wellness program is represented by $\beta_1 + \beta_4 * Exposure + \beta_5 + \beta_7 * Exposure$, or $(\beta_1 + \beta_5) + (\beta_4 + \beta_7) * Exposure$. The average effects for each group can be derived by evaluating this at the average level of exposure. We will evaluate whether any differences are statistically significant.

E. Worksite-level analyses

We complement our analyses at the individual level with analyses at the worksite level. Worksite-level data were generated by aggregating values for individuals up to their initial worksite. This aggregation was weighted by the number of hours each employee worked during the treatment period. The estimating equation below captures the framework of the worksite-level analyses.

$$Y_{kt} = \beta_0 + \beta_1 TREATMENT_{kt} + \beta_2 X_{kt} + \varepsilon_{kt} \tag{6}$$

In equation (6), the subscript k denotes a worksite. Analogous to the individual-level analyses, Y_{kt} represents an outcome for worksite k at time t . $TREATMENT_{kt}$ is a binary indicator of

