Full-time salary	4.7	7.0	21.3	11.6	12.1	21.7	11.5	11.4	21.8
Full-time hourly	37.4	44.3	66.6	38.6	52.4	66.8	49.0	53.6	66.4
Part-time hourly	57.9	48.7	12.1	49.8	35.5	11.4	39.5	35.0	11.8
Worker Type (%)									
Sales worker	43.2	45.3	23.2	38.4	39.0	22.3	36.2	39.3	23.3
Non-sales worker	45.9	41.8	52.4	46.4	42.8	52.8	47.4	43.7	51.6
Other worker	10.9	13.0	24.4	15.3	18.2	25.0	16.5	16.9	25.0

Notes: Table lists demographic characteristics for the sample covered by Cigna weighted by months of Cigna coverage. About a third of the total sample has Cigna coverage. Age is defined as age at the mid-point of the treatment period (June 2016). This is different from the balance table where age is defined as of December, 2014 (pre-treatment). Thus the means of age in this table are larger than those in the balance table across all samples.

Table 3: Impact on Employment

	Employee-level			Stably Employed Subsample			Worksite-level		
	Mean Value in Control Group (1)	Reduced Form (Linear) (2)	2SLS (Linear) (3)	Mean Value in Control Group (1)	Reduced Form (Linear) (2)	2SLS (Linear) (3)	Mean Value in Control Group (1)	Reduced Form (Linear) (2)	2SLS (Linear) (3)
Absenteeism (%)	2.23 (2.30) 41,376			3.39 (1.97) 13,000			2.90 (0.35) 135		
Performance Review (% ≤ 3)	46.59 (49.88) 27,150			63.64 (48.11) 12,916			65.94 (12.41) 135		
Tenure [§]	416.69 (399.87) 41,376			786.57 (376.96) 13,000			76.08 (4.35) 135		

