Notes: Table reports the coefficient on TREATMENT from estimating equation (1) by OLS (column 2), and the coefficient on PARTICIPATION from estimating equation (2) by IV (column 3). Standard errors are listed in parentheses. Column 1 reports the mean of each employment outcome in the control group for each sample (with standard deviation in parentheses, followed by the number of observations for each outcome). All regressions will include demographic and employment controls (age, sex, age-sex interactions, race/ethnicity, Cigna coverage status, full-time status, paid hourly status, and job category) and cluster standard errors at the worksite (for employee-level regressions). Employee-level and stably employed subsample control means are weighted by a weight that balances treatment and control on demographic characteristics. Worksite-level control means are not traditionally weighted: individual-level records are collapsed at the worksite-level and weighted by the total number of hours worked at each worksite. For worksite level results on tenure, the outcome was defined as the percent of total days at the worksite during the study period that was worked by employees at the worksite.

§ Tenure was defined as the number of days worked during the treatment period for the employee-level mean and stably employed subsample mean; it was defined as the percent of the entire treatment period worked by employees in the worksite-level mean.

Table 4: Impact on Medical & Pharmaceutical Spending and Utilization

	Employee-level			Stably Employed Subsample			Worksite-level (per 2000 work hours)		
	Mean in Control Group (1)	Reduced Form (Linear) (2)	2SLS (Linear) (3)	Mean in Control Group (1)	Reduced Form (Linear) (2)	2SLS (Linear) (3)	Mean in Control Group (1)	Reduced Form (Linear) (2)	2SLS (Linear) (3)
Medical Spending									
Total Spending	4800.57 (18559.82)			4721.85 (19056.92)			5044.74 (2994.54)		
Medical Utilization									
Number of Office visits	3.90 (4.47)			3.95 (4.33)			4.21 (0.93)		
Number of Hospitalizations	0.09 (0.40)			0.08 (0.36)			0.08 (0.05)		
Number of ER Visits	0.28 (0.75)			0.26 (0.61)			0.27 (0.11)		
Pharmaceutical Spending									
Total Spending	1237.60 (6921.32)			1227.32 (7115.67)			1317.72 (1145.17)		
Pharmaceutical Utilization									
Number of Distinct Medications	5.49 (6.44)			5.91 (6.54)			6.00 (1.30)		
Total Medication Months	11.20 (19.31)			11.41 (19.37)			12.39 (4.38)		
N	7,174			5,779			135		

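### Worksite-level tenure is averaged with hours-worked weights, so the measure can shrink, cancel or in some cases reverse a retention gain

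*Combined protocol and SAP*

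**What the plan says.** Section VI.E describes how individual values are aggregated to the employee's initial worksite: "This aggregation was weighted by the number of hours each employee worked during the treatment period". The Table 3 notes say of the worksite control means that "individual-level records are collapsed at the worksite-level and weighted by the total number of hours worked at each worksite". That wording could also describe weights between sites, but VI.E is explicit that the weight is each employee's hours.

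The Table 3 notes define worksite tenure twice. The body of the note says "the outcome was defined as the percent of total days at the worksite during the study period that was worked by employees at the worksite". The footnote says "it was defined as the percent of the entire treatment period worked by employees in the worksite-level mean". Neither wording exempts tenure from the hours weights.

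Table 3 gives control tenure as "416.69 (399.87) 41,376" (mean days, SD, N) at employee level and "76.08 (4.35) 135" (percent, SD, number of sites) at worksite level. The all-employee and stably employed columns use days with demographic balance weights, not hours weights. Section VI.C states that "tenure and time worked are among our primary outcomes".

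**The concern.** An employee who stays longer works more hours. Hours weighting therefore gives a long-tenure employee a large weight because the tenure is long, and a short-tenure employee almost none. When an early leaver stays a little longer, that employee's own value rises, but so does the weight on a value that is still well below the site average. The second effect can outweigh the first.

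The weight is also measured after randomization and can itself respond to the program. Tenure is named among the primary outcomes, and Table 3 is laid out to report a worksite-level effect on it. The worksite column could then differ from the employee-level columns, in size or even in sign, because of the weighting alone, and nothing in the table would tell the reader so.

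**Working it through.** **Inputs.** Employee-level control mean 416.69 days, SD 399.87; stably employed control mean 786.57 days; worksite control mean 76.08%, SD 4.35, 135 sites (all Table 3). The treatment period is "the 36-month period spanning January 2015 through December 2017" (Section VI), that is 365 + 366 + 365 = 1,096 days. Individual hours are not given, so days employed stand in for hours (assumption).

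**1. Which average gives the reported 76.08%?**
- Headcount: 416.69 / 1,096 = 38.0%.
- Weighted by days: M = Σt²/Σt = mean + SD²/mean = 416.69 + 399.87²/416.69 = 800.4 days; 800.4 / 1,096 = 73.0%.
- Stably employed, headcount: 786.57 / 1,096 = 71.8%.

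The reported value is about twice the headcount figure and exceeds even the stably employed mean. The day-weighted figure is close but not exact: 76.08 − 73.03 = 3.05 points short. Days are only a proxy for hours, so the gap is not an error in the plan. It does mean that the match is one of fit, not of exact reproduction.

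**2. How does M respond to longer tenure?** Moving one employee from t to t + d days changes M from Σt²/Σt to (Σt² + 2td + d²)/(Σt + d). This is a fall exactly when 2t + d < M. M is 800 days from the moments, or 0.7608 × 1,096 = 834 days from the reported value. For a small extension the turning point is M/2, about 400 to 417 days.

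Two-employee illustration: tenures of 100 and 1,096 days give (100² + 1,096²)/1,196 = 1,012.7 days, or 92.4%. Extending the first to 200 days gives (200² + 1,096²)/1,296 = 957.7 days, or 87.4%. The headcount mean rises from 54.6% to 59.1%.

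One extra day for everyone, without a cap, moves M by 2 − M/mean = 2 − 800.4/416.69 = +0.08 day, or about 0.00 with M = 834.

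**3. Scenarios.** Tenure is drawn from a beta distribution on 0 to 1,096 days matched to the mean and SD above (assumption). Changes are in percentage points of the period.

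| Change in tenure | Headcount mean | Hours-weighted |
|---|---|---|
| +60 days for everyone, capped | +5.1 | −0.2 |
| +60 days for those under 90 days | +1.9 | −3.1 |
| +60 days for those under 365 days | +3.0 | −3.7 |
| +60 days for those at 400 days or more | +2.0 | +3.6 |
| All tenures × 1.1, capped | +2.8 | +4.3 |
| 10% of those under 90 days stay to the end | +3.4 | +2.4 |

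**4. Lower exit rates with positions refilled.** Assume a fixed headcount, a daily exit hazard of 1/150 for the first 120 days and 1/1,500 after that. Cutting only the early hazard by 20%, in spells that start during the program, moves the headcount mean from 40.7% to 44.0% (+3.3) and the hours-weighted measure from 76.9% to 77.4% (+0.5). The sign is right, but most of the movement is lost.

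**5. Scale.** A rough unadjusted standard error from the site SD is 4.35 × √(1/25 + 1/135) = 0.95 points. With the 20 continuously treated sites of VI.E's base specification it is 4.35 × √(1/20 + 1/135) = 1.04. On this scale a fall of 3.1 points is about three standard errors, and a gain of 0.5 points is about half of one.

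**The case against.** A reader might infer that any real retention benefit would be reported as harm, or that the measure simply has the wrong sign for early turnover. The documents do not support that. Reversal requires that early leavers stay a bounded, modest time longer and then leave (2t + d below about 800 to 834 days). Proportional gains, gains among longer-tenure staff, early leavers who stay to the end and lower exit rates all raise the measure.

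The negative scenarios are also partly artificial. Days are counted inside the study window, so short tenures include late hires still employed in December 2017, who cannot gain days. With about 118 employees at a time (Section III) out of 304 per club over the study (Figure 2), 118/304 = 39% are on the rolls at any date. The beta scenarios also ignore that a retained employee delays a successor. The falls of 3.1 and 3.7 points are therefore illustrations, not forecasts.

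VI.E presents the worksite analyses as a complement, two other columns of Table 3 report tenure in plain days, and VI.C tests exit balance separately. A reversal would appear beside those results.

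All of this stands, and it limits the reach and severity of the point. It does not rescue the measure: a tenure outcome whose response to longer tenure can be positive, near zero or negative, depending on who stays and for how long, cannot be interpreted on its own.

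**Conclusion.** The point holds in a limited form and should be fixed. Worksite-level tenure is weighted by a post-randomization quantity that is close to the outcome itself, and the reported 76.08% is consistent with that and not with a headcount mean of about 38%. The consequence ranges from strong attenuation (+3.3 by headcount against +0.5) through cancellation (+5.1 against −0.2) to reversal in the particular case of modest extensions among early leavers. Some gains are not attenuated at all.

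The direction rule 2t + d < M is exact if hours are proportional to days employed. The scenario sizes also rest on the assumed beta shape or the assumed exit hazards. The defect is confined to the worksite-level tenure row of Table 3; the employee-level and stably employed columns do not carry it.

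**What to change.** In VI.E and the Table 3 footnote, exempt tenure from hours weighting. Define site tenure as the simple headcount mean, over all employees assigned to the site, of days employed divided by the full treatment period (1,096 days for every employee, not days since hire). Any extra day employed then raises the measure. Replace the two wordings in the Table 3 notes with this one definition, and recompute the control mean and SD. The mean should be about 38% for all employees; the exact site average needs the individual data.

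A separate worksite rule for one outcome has a precedent: Section IV.A2 sets distinct medications apart from the per-2,000-hours scaling, although that construction itself keeps hours weights.

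The cost is a sentence in VI.E, a revised footnote and a rerun of one row with existing data. Short-tenure hires then count fully, so the site mean may be noisier. The regression weights across sites need not change for this repair. The plan states that outcomes have not yet been compared between arms over the three-year window, so a change made before that comparison remains pre-specified.

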Notes: Employees are included if they answered at least 1 question on the PHA. Demographic characteristics are plausibly unaffected by the treatment. Demographics are taken from the Team Member database supplied by BJ's and based on the first entry for an individual during the treatment period. Age is defined as of December, 2014 (pre-treatment). Column 1 reports the means for employees in the treatment group while column 2 reports the means for the primary control employees. Treatment status is defined by the first worksite an employee appears in during the treatment period. Column 3 reports the p-value for the comparison between the employees at treatment worksites and the employees at primary control worksites. All regressions are weighted by a weight that balances treatment and control on demographic characteristics and cluster standard errors by worksite.

Panel C: Cigna Insured Subsample

	(1) Treatment (n=1385)	(2) Primary Control (n=1354)	(3) Primary + Secondary Control (n=7174)	(4) (1) vs (2) P value	(5) (1) vs (3) P value
Demographics					
Age (yrs)	42.7	42.1	42.6	0.321	0.836
Female (%)	44.4	43.8	44.6	0.768	0.949
Race (%)				0.996	>0.999
Black	16.9	14.9	17.7		
White	62.7	66.6	61.2		
Hispanic	14.7	14.9	15.9		
Other	5.6	3.7	5.2		

Notes: Employees are included if they had at least 1 month of Cigna health insurance coverage. Demographic characteristics are plausibly unaffected by the treatment. Demographics are taken from the Team Member database supplied by BJ's and based on the first entry for an individual during the treatment period. Age is defined as of December, 2014 (pre-treatment). Column 1 reports the means for employees in the treatment group while columns 2 and 3 report the means for the primary control employees and all control employees (primary and secondary), respectively. Treatment status is defined by the first worksite an employee appears in during the treatment period. Column 4 reports the p-value for the comparison between the employees at treatment worksites and the employees at primary control worksites and column 5 reports the p-value for the comparison between the employees at treatment worksites and all employees at control worksites. All regressions are weighted by a weight that balances treatment and control on demographic characteristics and cluster standard errors by worksite.

Panel D: Stably Employed Subsample

	(1)	(2)	(3)	(4)	(5)

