	Treatment (n=2344)	Primary Control (n=2378)	Primary + Secondary Control (n=13000)	(1) vs (2) P value	(1) vs (3) P value
Demographics					
Age (yrs)	39.0	38.1	38.7	0.193	0.623
Female (%)	47.4	47.7	46.9	0.905	0.747
Race (%)				0.998	>0.999
Black	20.5	18.1	20.3		
White	57.9	60.5	56.2		
Hispanic	16.2	17.4	17.7		
Other	5.4	4.0	5.8		
Employment					
Worker type (%)				>0.999	>0.999
FT salary	11.7	11.8	12.0		
FT hourly	36.2	37.3	38.2		
PT hourly	52.1	50.9	49.9		
Annual rate (\$)					
FT salary	49,304	47,910	48,301	0.178	0.218
FT hourly	24,933	24,237	24,773	0.285	0.764
PT hourly	10,142	9,944	10,027	0.220	0.430
Standard Hours Per Week				>0.999	>0.999
FT salary	40	40	40		
FT hourly	35.6	35.6	35.8		
PT hourly	20	20	20		
Job Category				>0.999	>0.999
Sales workers	38.1	38.3	37.8		
Laborers/Helpers	18.9	17.8	18.4		
Operatives	15.7	15.1	15.4		
Service workers	12.3	13.1	12.5		
First/Mid level officials	9.2	9.2	9.4		
Admin Support	3.8	3.9	4.2		
Other	2.1	2.6	2.2		
Health Insurance					
Ever Enrolled in Cigna (2014)	0.4	0.4	0.4	0.964	0.244
Months in Cigna	11.4	11.3	11.4	0.834	0.607
Total medical spending	5,476	3,634	4,659	0.135	0.493

Notes: Employees are included if they were part of the stably employed subsample. Health insurance variables are pre-randomization characteristics. Demographics and employment characteristics are taken from the Team Member database supplied by BJ's and based on the first entry for an individual during the treatment period. Age is defined as of December, 2014 (pre-treatment) and employees who were under 18 are excluded. Column 1 reports the means for employees in the treatment group while columns 2 and 3 report the means for the

primary control employees and all control employees (primary and secondary), respectively. Treatment status is defined by the first worksite an employee appears in during the treatment period. Column 4 reports the p-value for the comparison between the employees at treatment worksites and the employees at primary control worksites and column 5 reports the p-value for the comparison between the employees at treatment worksites and all employees at control worksites. All regressions are weighted by a weight that balances treatment and control on demographic characteristics and cluster standard errors by worksite.

Table 9: Balance Between Treatment and Control—Worksite Level

	(1)	(2)	(3)		
	Treatment	Primary Control	Primary + Secondary Control	(1) vs (2)	(1) vs (3)
	(n=25)	(n=25)	(n=135)	P value	P value

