Note: Control means and first stage estimates of the impact of TREATMENT on alternate definitions of PARTICIPATION. All regressions include demographic and employment controls (age, sex, age-sex interactions, race/ethnicity, full-time status, paid hourly status, and job category) and cluster standard errors at the worksite level. All samples other than the sample with Cigna coverage also include a control for whether or not the employee ever had Cigna coverage during the treatment period. Employee-level regressions are weighted by a weight that balances treatment and control on demographic characteristics. Standard errors shown in parenthesis and p-values in brackets.

Panel B: Employee-level—Stably Employed Sub-sample

	All		Surveyed		Cigna	
	(7) Control Mean	(8) Estimated First Stage	(9) Control Mean	(10) Estimated First Stage	(11) Control Means	(12) Estimated First Stage
Completed any module (%)	0.57	49.75 (2.82) [0.00]	3.90	79.22 (2.74) [0.00]	0.97	59.54 (3.24) [0.00]
Modules completed (#)	0.02	2.56 (0.21) [0.00]	0.15	5.41 (0.39) [0.00]	0.04	3.41 (0.29) [0.00]
3 or more modules (%)	0.35	35.04 (2.47) [0.00]	2.96	67.78 (3.39) [0.00]	0.61	45.79 (3.15) [0.00]
Average total incentive payment (\$)	0.75	97.62 (8.45) [0.00]	5.92	217.91 (15.74) [0.00]	1.54	163.36 (13.80) [0.00]
N	13,000	15,344	747	1,396	5,779	6,907

Note: Control means and first stage estimates of the impact of TREATMENT on alternate definitions of PARTICIPATION. All regressions include demographic and employment controls (age, sex, age-sex interactions, race/ethnicity, full-time status, paid hourly status, and job category) and cluster standard errors at the worksite level. All samples other than the sample with Cigna coverage also include a control for whether or not the employee ever had Cigna coverage during the treatment period. Employee-level regressions are weighted by a weight that balances treatment and control on demographic characteristics. Standard errors shown in parentheses and p-values in brackets.

Panel C: Worksite level

	All		Surveyed		Cigna	
	(1) Control Mean	(2) Estimated First Stage	(3) Control Mean	(4) Estimated First Stage	(5) Control Means	(6) Estimated First Stage
Completed any module (%)	0.22	28.19 (1.27) [0.00]	3.07	62.25 (1.89) [0.00]	0.91	57.29 (2.83) [0.00]
Modules completed (#)	0.01	1.17 (0.09) [0.00]	0.11	3.49 (0.22) [0.00]	0.03	3.18 (0.27) [0.00]
3 or more modules (%)	0.12	16.69 (1.12) [0.00]	2.27	46.65 (2.16) [0.00]	0.54	43.68 (2.76) [0.00]

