Appendix 1: Description of Phase 2 Modules and Incentives

Appendix 2: Determination of the Stably Employed Subsample

Appendix 1: Description of Phase 1 Modules and Incentives

Module 1

Take Charge of Your Health Rounds 1 and 2 (2/23/2015-3/27/2015, 4/13/2015-5/15/2015)

- **Summary:** These two five-week programs were presented as a series of webinars with corresponding PowerPoints designed to help employees who participate take their health care into their own hands. Topics covered included:
 - o how to choose a health plan and primary care physician,
 - o what to expect from a routine visit,
 - o routine tests and screenings and recommended frequencies,
 - o how to get the most from a doctor's visit,
 - o choosing generic medications over the corresponding brand name,
 - o staying healthy by eating well, staying active, sleeping enough, and managing stress, and
 - o primary care vs urgent care vs the emergency room and when to use each.
- **Incentive:** Employees who completed the webinars and returned the verification form received a \$25 BJ's gift card.

Module 2

Nutrition for a Lifetime (6/1/2015-7/10/2015)

- **Summary:** This six-week program was presented as a series of webinars with corresponding PowerPoints designed to help employees who participate achieve and maintain a healthy weight for life through the four pillars of health: nutrition, exercise, stress management, and sleep. Topics covered included:
 - o the negatives consequences of chronic stress and poor sleep habits and techniques to manage stress and improve sleep,
 - o good nutrition, including an overview on the different food groups and the amounts of each recommended per day,
 - o reasons for making exercise a priority and how to get the most out of a workout,
 - o foods to limit and foods to increase in a diet,
 - o appropriate portion sizing, especially for weight loss and weight maintenance, and
 - o choosing the right fats and the importance of fiber.
- **Incentive:** Employees with Cigna coverage received a \$150 Weight Management Reimbursement and all other employees received a \$50 gift card if they completed 5 out of the 6 webinars and returned the verification form.

Modules 3 and 4

Club Cardio Challenge Rounds 1 and 2 (8/10/2015-9/25/2015, 9/26/2015-11/16/2015)

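### The claims analyses select employees on Cigna coverage during the treatment period, which the program could affect, and the plan neither tests nor bounds the resulting risk of selection bias

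*Combined protocol and SAP*

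**What the plan says.** - **Sample rule.** Section IV.A2 limits claims outcomes to employees in a Cigna plan. The note to Table 8, Panel C gives the rule: "Employees are included if they had at least 1 month of Cigna health insurance coverage". It states no period.
- **Period.** The Table 10 note says that every sample except the Cigna one includes "a control for whether or not the employee ever had Cigna coverage during the treatment period".
- **Rewards.** Appendix 1, Module 2 gave employees with Cigna coverage a $150 "Weight Management Reimbursement and all other employees received a" $50 gift card. Modules 3/4, 10/11 and 12 each carried a further $150 reimbursement open only to Cigna members.
- **Content.** Module 1 topics included "how to choose a health plan and primary care physician".
- **Safeguards.** Sections V.A and VI.C handle entry to the firm with the stably employed subsample, and exit from the firm with a balance test and a bounding exercise. Neither mentions entry to or exit from the Cigna plan.
- **Balance.** Section V.B says the prevalence of Cigna insurance is balanced in all analytical subsamples. The only test of coverage shown is 2014 enrolment in Table 8, Panel D: 0.4 in each group, p = 0.964 against primary controls and 0.244 against all controls.

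**The concern.** The plan already recognizes that a sample whose membership may respond to treatment can break the comparison that randomization set up. It applies this to employment but not to insurance. An employee can be in the stably employed subsample and still enter the claims sample only by taking up Cigna after launch.

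If the program drew in, or kept, employees with different spending, the treated and control claims samples would differ for reasons other than an effect on spending, and the bias could go either way. Total medical spending is one of the main outcomes, and the stably employed subsample does not remove this problem.

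A separate and smaller matter is the treatment-period coverage indicator used as a covariate. Section V.B prefers job characteristics fixed before the intervention, and Section VI.A measures employment covariates at baseline for the stably employed. An indicator measured after randomization departs from both, and the covariate list in Section VI.A does not include it.

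**Working it through.** **1. Which period defines the sample.** The control N in Table 8, Panel C (7,174) is also the control N in Table 4 and in the Cigna column of Table 10, whose note defines coverage over the treatment period. The stably employed control N (5,779) likewise agrees between Tables 4 and 10.

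**2. Treatment Ns.** Table 10 gives control and total N; subtraction gives treatment N. This reproduces Table 8 wherever it can be checked:
- all employees: 48,664 − 41,376 = 7,288
- PHA: 2,793 − 1,454 = 1,339
- Cigna: 8,559 − 7,174 = 1,385
- stably employed: 15,344 − 13,000 = 2,344

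For the stably employed with Cigna, 6,907 − 5,779 = 1,128.

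**3. Coverage by arm (raw counts).**

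| Sample | Treatment | Control | Gap (points) |
|---|---|---|---|
| Stably employed, v all control | 1,128/2,344 = 48.1% | 5,779/13,000 = 44.5% | 3.7 |
| All employees, v all control | 1,385/7,288 = 19.0% | 7,174/41,376 = 17.3% | 1.7 |
| All employees, v primary control | 1,385/7,288 = 19.0% | 1,354/7,377 = 18.4% | 0.6 |

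**4. Could the stably employed gap be chance?** Ignoring clusters, z = 3.29 and p = 0.001. The documents give no ICC, so I assume a range and inflate each arm's variance by 1 + (m − 1) × ICC, with m = 2,344/25 ≈ 94 and 13,000/135 ≈ 96.

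| Assumed ICC | z | p |
|---|---|---|
| 0.005 | 2.71 | 0.007 |
| 0.01 | 2.36 | 0.018 |
| 0.02 | 1.94 | 0.053 |
| 0.03 | 1.68 | 0.093 |
| 0.05 | 1.38 | 0.17 |

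The p-value passes 0.05 at an ICC of about 0.019. For all employees against primary controls, p = 0.31 even without clustering.

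**5. How much race could explain.** Relative coverage by race is the share in the Cigna control sample (Panel C) divided by the share among all controls (Panel A.2): Black 17.7/25.9 = 0.68, white 61.2/50.1 = 1.22, Hispanic 15.9/17.2 = 0.92, other 5.2/6.8 = 0.76. Applied to the unweighted race mix in Panel A.1, these average 1.034 in treatment and 0.995 in control, a ratio of 1.039. The predicted gap is 0.039 × 17.3 ≈ 0.7 of the 1.7 points. Unweighted race is not shown for the stably employed. If the race difference there equals that among all employees, the Table 2 stable-sample ratios predict about 1.3 of the 3.7 points.

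**6. Possible size.** The excess is 1,128 − 2,344 × 0.4445 = 86 employees, or 86/1,128 = 7.6% of the treated claims sample. Suppose all 86 are an added group whose annual spending differs by $2,000 to $5,000 (my assumption). The treated mean then shifts by 0.076 × 2,000 ≈ $150 to 0.076 × 5,000 ≈ $380, which is 3% to 8% of the control mean of $4,721.85. The unclustered standard error of the difference is 19,056.92 × √(1/1,128 + 1/5,779) ≈ $620.

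**The case against.** A reader might infer from 48.1% v 44.5% that the program raised Cigna enrolment, or that the spending estimate is biased. The documents support neither.

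- The percentages come from raw counts, whereas the planned models are weighted and race-adjusted. Race accounts for part of the gap.
- Against primary controls the full-sample gap is only 0.6 points.
- Part may predate the program. A p-value of 0.244 for 2014 enrolment would fit a baseline gap of about 1.3 to 2.2 points, using standard errors like those above at ICC 0 to 0.02. Its sign is not shown.
- The incentive is modest. Table 10 puts the effect on total incentive payments among Cigna enrollees at $148.83 over three years, about $50 a year and for all rewards. The documents give no premiums or enrolment rules from which to judge whether that would change behavior.
- The illustrative bias is at most about 0.6 of an unclustered standard error (380/620).

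All of this stands against the stronger reading. It does not answer the design point: the sample is conditioned on a variable measured after randomization, and the balance statement in Section V.B has only 2014 enrolment shown behind it. Nor does job mix explain the gap. The treatment arm has slightly more part-time staff (52.1% v 49.9%), who are less often covered.

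A reader might also infer that the coverage covariate biases the spending models. It does not enter them: the Table 4 note does not list it, and Table 10 leaves it out for the Cigna sample. Tables 3, 5 and 6 list Cigna coverage status without a period, so it cannot be said that they adjust for treatment-period coverage.

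Finally, replacing the planned sample with 2014 enrollees would not be clearly better. Some would later lose coverage, and 2014 spending itself differs between groups ($5,476 treatment, $4,659 all control, $3,634 primary control; p = 0.493 and 0.135).

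**Conclusion.** The concern holds as a risk of selection bias. The claims analyses, including the stably employed one, depend on coverage that the program had a plausible route to affect, and no planned analysis examines entry to or exit from the plan.

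The 3.7-point raw gap is a reason to look, not proof of an effect. The p-value runs from about 0.007 to 0.17 over the assumed ICCs, and race may account for over a third of the gap (1.3 of 3.7 points, under the assumption stated). The $150 to $380 shift rests on treating every excess enrollee as induced and on an assumed spending difference; it is material but not decisive. The covariate is a separate, smaller departure from the plan's preference for baseline characteristics. It is certain only in Table 10.

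**What to change.** 1. Report Cigna coverage during the treatment period by arm, weighted and with standard errors clustered by worksite, for all employees and for the stably employed.
2. Keep the planned stably employed claims analysis and pre-specify beside it one restricted to employees enrolled in Cigna in 2014, which is already held. Extend the bounding exercise in Section VI.C to differential entry to and exit from the plan.
3. In Table 10, replace the treatment-period coverage covariate with 2014 enrolment for the stably employed, and drop it for the full sample. Do the same in Tables 3, 5 and 6 if their coverage status is also measured during treatment; if not, state the period.

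**Cost.** SAP wording, one extra table and one extra set of models. The added analysis leaves out employees who first enrolled after 2014, so it describes a narrower group. It is also smaller, by an amount the documents do not fix. A 2014 share that rounds to 0.4 lies between 0.35 and 0.45, so the combined sample is between 0.35 × 15,344 ≈ 5,370 and 0.45 × 15,344 ≈ 6,905, against 6,907 now. That is up to about a fifth fewer (22%), before any later loss of coverage.
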